#### • TERTIARY END USERS (FORMAL CAREGIVERS):

- Over 1 year experience;
- Psychologist, neurologist, occupational therapist, nurses from health care facilities or paid by the participants.

#### 3.2.5 Exclusion criteria

The exclusion criteria consist of

- Concomitant participation in other studies;
- Lack of written informed consent;
- Not meeting the inclusion criteria
- Previous diagnosis of dementia or other neurodegenerative diseases;
- Psychiatric illnesses that could affect cognitive functioning;
- Chronic neurological or systemic disorders not compensated pharmacologically that could affect cognitive functioning;

#### 3.3 Channels of recruitment

To ensure that the right participants are included in the evaluations, each partner must have its own recruitment technique, and ensure that the inclusion criteria mentioned above are met. Several channels are available for this purpose, and everyone is free to proceed in the easiest perceived way. Each pilot site should give priority to those who participated in the laboratory tests

#### 3.3.1 Italy (INRCA)

Regarding the recruitment channel, Italian partners will use the contact list of their neurology unit and Alzheimer day-care centre to communicate with potential participants of previous projects and initiatives, as well as with other people who might be interested in contributing to the project evaluations. This method makes possible to be in contact with clients met before and with whom a relationship of trust has been already established.

#### 3.3.2 Switzerland (HUG)

Swiss partners will contact the different units of the HUG in neurology, the memory center and the day care center in Geneva. They will be contacted to know if they are interested to participate in the development of the project by introducing us to potential participants to evaluate the project.

#### 3.3.3 Norway (KARDE)

Karde is in contact with Arendal municipality and test users will mainly be recruited from two daycentres in Arendal. Information meetings will be conducted in collaboration with Arendal

#### 3.4 Outcomes

In this section the outcomes measured throughout the field trials are reported. The main focus of the engAGE project, and so of the field trial, is the perceived stability of cognitive capabilities of people with MCI. In second place, the acceptance and the usability of the platform, as well as the caregivers' benefits have to be assessed. Thus, the outcomes are the following:

- PRIMARY END USERS (SMCI):
  - Primary outcome: perceived stability of cognitive status (MAC-Q)

- Secondary outcomes: Adherence to intervention, wellbeing, quality of life, acceptance and usability, cost-benefit analysis
- SECONDARY END USERS (INFORMAL CAREGIVERS):
  - Reduction/stability of informal caregiver's burden
  - Improvement of well-being, psychological status
  - Acceptability, usability and affordability of the solution
- TERTIARY END USERS (FORMAL CAREGIVERS):
  - Improving quality of work.

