## 3 Field trial

#### 3.1 Study design

The field trial will be conducted as a controlled longitudinal study, with a before and after design where the observations are made on a series of enrolled individuals, receiving the intervention described below with control group, with data collected before and after the installation and use of the technical solution. The goal of trial evaluation is to assess the engAGE technology integration into everyday life, effectiveness on mitigating the cognitive decline, acceptance over six months, security and reliability of proposed solutions as well as the business perspective reflecting the market demand (including the willingness to pay) for the developed services. The field trial procedure will be divided into two different phases, after the recruitment of the participants: Baseline evaluation (T0, M1) and Final evaluation (T1, M6), with the aim of collecting data as follows:

- **Recruitment phase** (R): the recruitment protocol will include general information on the subjects, in particular, health status and cognitive condition. The information will be collected with the help of the caregiver/family member if needed.
- **Baseline evaluation** (T0, M1): that will consist of the first real contact with the users and their families, before the start of the field trial.
- **Mid-term evaluation** (T1, M3): the aim of mid-term evaluation is to collect useful information on the use of the engAGE platform after a short period of use for detecting and analysing the technology acceptance and usability issues.
- Final evaluation (T2, after six months of use, M6): the aim of this phase is to collect useful information on the whole benefits perceived by the users after a meaningful period of use of the system. The final evaluation will be conducted after the system de-installation, to detect and analyse the impact of the system in the daily life of the older people and their family. Moreover, the final evaluation aims to gain knowledge on elderly technology acceptance and usability issues to be compared with mid-term results (T1), in order to assess the longterm acceptance and provide methodological approach for further studies in the field.

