#### 3.2.4 Inclusion criteria

- PRIMARY END USERS (SMCI):
  - over 65 years old;
  - MoCA score 21 25;
  - MAC-Q ≥ 25;
  - Reisberg scale 2 4;
  - Clinical Frailty Scale score 1 3;
  - 4-items GDS score  $\leq$  1.
- SECONDARY END USERS (INFORMAL CAREGIVERS):
  - Over 18 years old;
  - Primary informal caregiver of the user (see the user at least 2 times per week);

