#### 3.5 Scales and tools

In this section the questionnaires/scales asked to the end users are presented in the following tables, by indicating also at which time of the intervention a questionnaire/scale is asked.

Table 5. Questionnaires and scales asked to the senior with MCI during the field trial

PROTOCOL of QUESTIONNAIRES for SMCI	R	то	Т1	Т2
Socio-demographics checklist*		х		
Montreal Cognitive Assessment (MoCA) [IT - SW]	Х			х
Reisberg Scale	Х			
4-items Geriatric Depression Scale (GDS)	х			
Clinical Frailty Scale	х			
Memory Assessment Clinics – Questionnaire (MAC-Q)	х			х
Adherence to the system use (to be collected technically)			х	х
UCLA loneliness scale (social connectedness)		х		х
Warwick-Edinburgh Mental Wellbeing Scale (WEMWBS)		х		х
EQ-5D-5L (VAS)		х		х
Unified theory of acceptance and use of technology (UTAUT)			х	х
Quality of Life–Alzheimer's Disease (QoL-AD)		Х		х
System Usability Scale (SUS)			х	х

Semi-structured interview on acceptance, usability, willingness to pay		х	х	
--	--	---	---	--

PROTOCOL of QUESTIONNAIRES for IC/FC	R	то	Т2
Socio-demographics checklist	Х		
Zarit Burden Interview		х	Х
Adherence to the system use (to be collected technically)			х
UCLA loneliness scale (social connectedness)		х	х
Warwick-Edinburgh Mental Wellbeing Scale (WEMWBS)		х	х
EQ-5D-5L		х	Х
System Usability Scale (SUS)			Х
Semi-structured interview on acceptance, usability, willingness to pay, quality of work			х

Table 6. Questionnaires and scales for formal and informal caregivers

The quantitative tools are all standardized, and they are:

The **Montreal Cognitive Assessment (MoCA)** [1] is a widely used screening assessment for detecting cognitive impairment. The MoCA is a one-page 30-point test administered in approximately 10 minutes. The test and administration instructions are available for clinicians online. The test is available in 46 languages. The MoCA assesses several cognitive domains: the short-term memory recall task (5 points), visuospatial abilities (4 points), alternation task (1 point), verbal abstraction task (1 point), attention, concentration, and working memory (6 points), language (6 points), abstract reasoning (2 points), and orientation to time and place (6 points).

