#### 3.7 Work hypothesis

#### Work hypothesis

In this section, the hypothesis is presented along with solutions to measure the impact on those aspects.

- 1. Is there any improvement in the cognitive status?
  - Comparison of MAC-Q (before and after)
    - between groups (EG Vs CG)
    - o intra-group (EG)
- 2. Is the system usable for people with MCI?
  - Analysis of SUS in the EG
  - Analysis of UTAUT in the EG
  - stratifying for MCI
- 3. Is it the system effective in supporting lifestyle of people with MCI and their carers?
  - Adherence to the system to be assessed technically:
    - $\circ \quad \text{Nr. of interactions}$
    - o Nr. planned activities respected
- 4. And the quality of life of the participants?

- Comparison of QoL and WEMBS (before and after)
  - between groups (EG Vs CG)
  - o intra-group (EG)
- For Carers: Comparison of QoL and ZARIT (before and after)
  - between groups (EG Vs CG)
  - o intra-group (EG)
  - improvement of quality of work for Formal carers (from semi structured interview)
- 5. From semi-structured interview:
  - analysis of single modules' effectiveness/perception;
  - cost-benefit analysis;
  - willingness to pay.

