#### MONTREAL COGNITIVE ASSESSMENT (MOCA)

#### **REISEBERG SCALE**

Level	Clinical characteristics
1 No cognitive decline	No subjective complaints of memory deficit. No memory deficit evident on clinical interview.
2 Very mild cognitive decline (Age Associated Memory Impairment)	Subjective complaints of memory deficit, most frequently in following areas: (a) forgetting where one has placed familiar objects; (b) forgetting names one formerly knew well. No objective evidence of memory deficit on clinical interview. No objective deficits in employment or social situations. Appropriate concern with respect to symptomatology.
3 Mild cognitive decline (Mild Cognitive Impairment)	Earliest clear-cut deficits. Manifestations in more than one of the following areas: (a) patient may have gotten lost when traveling to an unfamiliar location; (b) coworkers become aware of patient's relatively poor performance; (c) word and name finding deficit becomes evident to intimates; (d) patient may read a passage or a book and retain relatively little material; (e) patient may demonstrate decreased facility in remembering names upon introduction to new people; (f) patient may have lost or misplaced an object of value; (g) concentration deficit may be evident on clinical testing. Objective evidence of memory deficit obtained only with an intensive interview. Decreased performance in demanding employment and social settings. Denial begins to become manifest in patient. Mild to moderate anxiety accompanies symptoms.
4 Moderate cognitive decline (Mild Dementia)	Clear-cut deficit on careful clinical interview. Deficit manifest in following areas: (a) decreased knowledge of current and recent events; (b) may exhibit some deficit in memory of ones personal history; (c) concentration deficit elicited on serial subtractions; (d) decreased ability to travel, handle finances, etc. Frequently no deficit in following areas: (a) orientation to time and place; (b) recognition of familiar persons and faces; (c) ability to travel to familiar locations. Inability to perform complex tasks. Denial is dominant defense mechanism. Flattening of affect and withdrawal from challenging situations frequently occur.

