#### MONTREAL COGNITIVE ASSESSMENT (MOCA)

MEMORY ASSESSMENT CLINICS-QUESTIONNAIRE (MAC-Q)

As compared to when you were in high school or college, how would you describe your ability to perform the following tasks involving your memory?

Activities	Much better now	Somewhat better now	About the same	Somewhat poorer now	Much poorer now
Remembering the name of a person just introduced to you	1	2	3	4	5
Recalling telephone numbers or zip codes that you use on a daily or weekly basis	1	2	3	4	5
Recalling where you put objects (such as keys) in your home or office	1	2	3	4	5
Remembering specific facts from a newspaper or magazine article you have just finished reading	1	2	3	4	5
Remembering the item(s) you intend to buy when you arrive at the grocery store or pharmacy	1	2	3	4	5
In general, how would you describe your memory compared to the past?	2	4	6	8	10

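### Cognitive status is to be judged only by self-rated MAC-Q from participants who know their arm, while MoCA, repeated at six months in Italy and Switzerland, has no named outcome or between-arm analysis

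*Combined protocol and SAP*

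**What the plan says.** All references are to the combined protocol and SAP.

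- **Goal (3.1).** The aims include "effectiveness on mitigating the cognitive decline", alongside everyday integration, acceptance, security and reliability, and market demand. The same section calls the trial a pilot and promises only a partial evaluation of effectiveness on cognition.
- **Outcomes (3.4).** "Primary outcome: perceived stability of cognitive status (MAC-Q" is followed by "Secondary outcomes: Adherence to intervention, wellbeing, quality of life, acceptance and usability, cost-benefit analysis". No cognitive test is listed.
- **Hypothesis 1 (3.7).** "Is there any improvement in the cognitive status" is to be answered by MAC-Q before and after, between groups and within the experimental group (EG). The word perceived does not appear there.
- **Schedule (3.5, Table 5).** "Montreal Cognitive Assessment (MoCA) [IT - SW" is marked at R and T2, and the T2 forms for seniors in Annex 3 include "MONTREAL COGNITIVE ASSESSMENT (MOCA" again.
- **Eligibility (3.2.4).** "MoCA score 21 25" (that is, 21 to 25) is the only stated use of the score. It carries no site exception.
- **Analysis (4.1).** MAC-Q is the only endpoint named. The rest is generic: pre/post comparisons of variables, and correlations of MAC-Q sub-scales with other rating scales.
- **Arms (3.6, 3.6.1).** EG has robot sessions and daily tablet use; the control group (CG) has a booklet of home activities.

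**The concern.** The question asked and the measure chosen do not match. MAC-Q asks participants to compare their own memory with an earlier period of life. A participant who has spent six months with a robot and a tablet, and knows it, may rate memory more favourably whether or not performance has changed. A MAC-Q difference between arms therefore cannot separate a cognitive effect from expectation, and hypothesis 1 as worded invites the cognitive reading.

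MoCA does not rest on the participant's opinion of his or her memory, and it is already scheduled at both ends of the study at two sites. Eligibility explains its use at recruitment but not its repetition at T2. With no role fixed in advance, it could be left out of the report, or brought in only if it happens to favour the system.

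**Working it through.** **1. Where each measure appears**

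| Place | MAC-Q | MoCA |
|---|---|---|
| 3.2.4 eligibility | yes | yes |
| 3.4 outcomes | primary | absent |
| 3.5 Table 5 | R and T2 | R and T2, Italy and Switzerland |
| 3.7 hypothesis 1 | only measure | absent |
| 4.1 named endpoint | yes | absent |

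The Reisberg scale is a clinical staging done at R only. Game scores and the machine-learning assessment are performance data, but they come from using the platform, so the booklet group has none, and neither is a listed outcome. MoCA is thus the only performance-based test at follow-up in both arms. For CG this reads the T6 evaluation in 3.6.1 as the six-month T2 visit.

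**2. Numbers available for MoCA**

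The plan gives no alpha, power, effect size or SD, so there is no calculation to reproduce. From Table 2:

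- EG, all sites: 20+20+8 = 48 to 22+23+10 = 55. Adding CG of at least 30 gives 78 to 85, which brackets the stated 80.
- EG in Italy and Switzerland: 20+20 = 40 to 22+23 = 45. CG at the minimum of 10 per site: 20.
- Total: 60 to 65, or 60/78 = 77% and 65/85 = 76% of the trial.

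**3. Unadjusted precision at T2 (no dropout)**

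The half-width of the 95% CI in SD units is c × √(1/n_EG + 1/n_CG), with c from 1.96 (normal) to 2.00 (t).

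- 40 vs 20: √(0.0250+0.0500) = 0.274, giving 0.54 to 0.55.
- 41 vs 20: √(0.0244+0.0500) = 0.273, giving 0.53 to 0.55.
- 45 vs 20: √(0.0222+0.0500) = 0.269, giving 0.53 to 0.54.

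So about 0.54 SD. If the T2 SD is 2.5 to 3 points (assumed), that is 0.54×2.5 = 1.4 to 0.54×3 = 1.6 points. If 20% were lost in each arm (assumed), it becomes 0.54/√0.8 = 0.60 SD.

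**4. Gain from baseline adjustment**

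The half-width shrinks by √(1−r²), where r = b × SD_baseline/SD_T2 and b is the slope of T2 on baseline MoCA. Entry is limited to 21–25, so the baseline SD is at most 2.0 (half at each end), and √2 = 1.41 if the five values are equally common.

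- With baseline SD 1.41, r = 0.5 needs b = 0.5×2.5/1.41 = 0.89 to 0.5×3/1.41 = 1.06. That is optimistic for a test with measurement error. It would give 0.54×0.866 = 0.47 SD.
- With b = 0.5 (assumed), r = 0.28 to 0.24, and the half-width falls only to about 0.52 SD.

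**5. Detectable difference**

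Assuming two-sided alpha 0.05, 80% power and no dropout: (1.96+0.84) × √(1/20+1/40) = 0.77 SD, or 0.75 SD with 45 in EG. Power for a true 0.5 SD difference is about 45–46%.

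**The case against.** **The scope is already limited.** Section 3.1 calls the study a pilot, mainly about perceived usefulness and usability, and 3.4 openly names a perceived outcome. This stands: MAC-Q is a deliberate choice and can remain primary. What it does not cover is 3.1 naming cognitive decline and 3.7 asking about cognitive status with no such limit.

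**Section 4.1 could reach MoCA.** A reader might infer that the MoCA data will certainly go unused. The documents do not show that: the generic pre/post comparisons and the correlations with other scales could include it. Neither sets out a between-arm MoCA contrast, so the gap is one of specification.

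**Loss of insight.** A reader might infer from the Reisberg table ("Denial is dominant defense mechanism" at stage 4, an eligible stage) that worsening participants would score as improved on MAC-Q. The documents do not support building on this. Entry requires MAC-Q of at least 25, which tends to screen out people who deny memory problems. Diagnosed dementia is excluded, and at stage 3 denial is only said to begin. Reduced insight would also affect both randomised arms, with no stated reason to favour EG.

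**Amount of contact.** The planned EG activity is (2×1 + 7×0.5) × 26 = 143 hours, and a reader might take this as extra contact. Of it, 3.5×26 = 91 hours is home tablet use with the informal caregiver and 2×26 = 52 hours is supervised at the centre. CG has home activities of unstated length, and section 5.1, which covers CG too, speaks of daily researcher contact. The documents do not quantify a contact difference.

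**MoCA has its own weaknesses.** It is imprecise here, is not scheduled in Norway, and is given by an interviewer who may know the allocation. All of this stands, and it limits MoCA to a supportive role.

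**Conclusion.** The point holds. Hypothesis 1 and the goal in 3.1 concern cognitive status and decline, but the only listed evidence is a self-rating by participants who cannot be unaware of their arm. The scheduled test that could inform the question has no named outcome or between-arm analysis. That the trial is open is inferred from the nature of the arms and the absence of any blinding text; the documents do not use the word.

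The MoCA estimate would carry a half-width of about 0.54 SD unadjusted, with perhaps little gain from adjustment. This takes the Table 2 headcounts at face value (CG at its minimum) and assumes no dropout. It can show which effects are compatible with the data but cannot confirm or exclude a modest one. For the same reason, agreement in direction between MoCA and MAC-Q should not license a cognitive claim: if MoCA were unaffected and independent of MAC-Q, the directions would agree about half the time.

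**What to change.** 1. In 3.4, add MoCA at T2 as a supportive secondary outcome for the sites that collect it.
2. In 3.7 and 4.1, specify the comparison: EG versus CG at T2 by ANCOVA with baseline MoCA, arm and site, reported as a difference with its 95% CI and described as not confirmatory.
3. Reword hypothesis 1 so that MAC-Q answers a question about perceived memory. Base any statement on cognitive status or decline on the MoCA estimate and CI, not on agreement in direction.
4. Reconcile the site label on MoCA in Table 5 with the MoCA inclusion criterion in 3.2.4, which has no site exception, and with 3.2.3, which says that no personal medical information is collected in Norway.
5. Where feasible, have MoCA at T2 given by an assessor unaware of allocation; otherwise state that raters knew it.

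Items 1 to 4 cost wording only, with no new visit or instrument; item 5 may need some staffing. The price is an imprecise secondary result that leaves out Norway. If the sponsor prefers not to analyse MoCA between arms, the minimum is to confine every cognitive conclusion to perceived memory and to state why MoCA is repeated at T2.

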#### 3.5 Scales and tools

In this section the questionnaires/scales asked to the end users are presented in the following tables, by indicating also at which time of the intervention a questionnaire/scale is asked.

Table 5. Questionnaires and scales asked to the senior with MCI during the field trial

PROTOCOL of QUESTIONNAIRES for SMCI	R	то	Т1	Т2
Socio-demographics checklist*		х		
Montreal Cognitive Assessment (MoCA) [IT - SW]	Х			х
Reisberg Scale	Х			
4-items Geriatric Depression Scale (GDS)	х			
Clinical Frailty Scale	х			
Memory Assessment Clinics – Questionnaire (MAC-Q)	х			х
Adherence to the system use (to be collected technically)			х	х
UCLA loneliness scale (social connectedness)		х		х
Warwick-Edinburgh Mental Wellbeing Scale (WEMWBS)		х		х
EQ-5D-5L (VAS)		х		х
Unified theory of acceptance and use of technology (UTAUT)			х	х
Quality of Life–Alzheimer's Disease (QoL-AD)		Х		х
System Usability Scale (SUS)			х	х

Semi-structured interview on acceptance, usability, willingness to pay		х	х	
--	--	---	---	--

PROTOCOL of QUESTIONNAIRES for IC/FC	R	то	Т2
Socio-demographics checklist	Х		
Zarit Burden Interview		х	Х
Adherence to the system use (to be collected technically)			х
UCLA loneliness scale (social connectedness)		х	х
Warwick-Edinburgh Mental Wellbeing Scale (WEMWBS)		х	х
EQ-5D-5L		х	Х
System Usability Scale (SUS)			Х
Semi-structured interview on acceptance, usability, willingness to pay, quality of work			х

Table 6. Questionnaires and scales for formal and informal caregivers

The quantitative tools are all standardized, and they are:

The **Montreal Cognitive Assessment (MoCA)** [1] is a widely used screening assessment for detecting cognitive impairment. The MoCA is a one-page 30-point test administered in approximately 10 minutes. The test and administration instructions are available for clinicians online. The test is available in 46 languages. The MoCA assesses several cognitive domains: the short-term memory recall task (5 points), visuospatial abilities (4 points), alternation task (1 point), verbal abstraction task (1 point), attention, concentration, and working memory (6 points), language (6 points), abstract reasoning (2 points), and orientation to time and place (6 points).

The **Reisberg Scale** [2] consists of 7 major clinical stages. It is used by clinicians and in care settings, but may be especially helpful for caregivers, as it is noticeably detailed regarding the general abilities of an individual at each stage and provides information about what to expect at different stages. The scores go from no cognitive decline (1) to very severe cognitive decline (7), through stages 2, 3, and 4 that are respectively: Very mild cognitive decline (age-associated memory impairment), mild cognitive impairment, and moderate cognitive decline.

The **4-items Geriatric Depression Scale (GDS)** [3] is a 4-items scale whose answers are yes or no. If all the items are answered negatively then the depression is excluded; if only one item is answered positively then the situation is uncertain; if at least 2 items are answered positively, the patient is depressed. Thus, this scale is easy and quick, and very useful in excluding depression.

The **Memory Assessment Clinics – Questionnaire (MAC-Q)** [4] is a 6-item scale that uses a 5-item Likert scale from "much better now"=1 to "much worse now"=5, and the last question scores double. The questionnaire asks the person to compare his or her memory with a previous period to measure age-related memory decline. Five items address specific situations frequently reported as problematic by those who experience memory loss with age. One item is a global item assessing general memory decline. A cutoff of 25 points or more indicates that the individual has a memory disorder.

**Clinical Frailty Scale (CFS).** [5] This descriptive scale divides the older participants into 9 classes based on the information provided by them and their relatives: between 1 and 3 the patient is non-frail, pre-frail if 4, he is frail from 5 to 9.

The **UCLA scale** [10] is a 20-item scale designed to measure one's subjective feelings of loneliness as well as feelings of social isolation. Participants rate each item as either O ("I often feel this way"), S ("I sometimes feel this way"), R ("I rarely feel this way"), N ("I never feel this way").

**EQ Visual Analogue Scale (EQ VAS)** [11] records the respondent's self-rated health on a 20 cm vertical, visual analogue scale with end-points labelled 'the best health you can imagine' and 'the worst health you can imagine'. This information can be used as a quantitative measure of health as judged by the individual respondents.

The **Warwick-Edinburgh Mental Wellbeing Scales (WEMBS)** [12] is used to enable the measuring of mental wellbeing in the general population. The 14-item scale WEMWBS has 5 response categories, summed to provide a single score. The items are all worded positively and cover both feeling and functioning aspects of mental wellbeing, thereby making the concept more accessible. The scale has been widely used nationally and internationally for monitoring, evaluating projects and programmes and investigating the determinants of mental wellbeing.

The **Unified Theory of Acceptance and Use of Technology (UTAUT)** [7] is a 20-item questionnaire that examines the acceptance of technology, determined by the effects of performance expectancy, effort expectancy, social influence and facilitating conditions.

The **Quality of Life – Alzheimer's Disease (QoL-AD)** [13] uses a scale of 1–4 (poor, fair, good, or excellent) to rate a variety of life domains, including the patient's physical health, mood, relationships, activities, and ability to complete tasks.

The **Zarit Burden Interview (ZBI)** is a caregiver self-report measure [9], containing 22 items. Each item on the interview is a statement which the caregiver is asked to endorse using a 5-point scale. Response options range from 0 (Never) to 4 (Nearly Always).

The **System Usability Scale (SUS)** [8] is a reliable tool for measuring usability. It consists of a 10-item questionnaire with five response options for respondents, from 'Strongly agree' to 'Strongly disagree'. It allows for evaluation of a wide variety of products and services, including hardware, software, mobile devices, websites and applications. It is easy to administer to participants and can be used on small sample sizes with reliable results and can effectively differentiate between usable and unusable systems.

Finally, a **semi-structured Interview** to evaluate the formal/informal caregivers' perspective on acceptability, usability and demand & cost information is built ad hoc, as the interview for the SMCI on usability and acceptability.

